2.2 Safety objectives and endpoints

Safety objective:

To evaluate the safety of *Sculptra* for correction of wrinkles in the décolletage area. Safety endpoints:

- 1. Incidence, intensity, time to onset and duration of Adverse Events (AE)s collected throughout the study period.
- 2. Incidence, intensity, time to onset and number of days of pre-defined expected post-treatment events collected using subject diaries for 28 days from each treatment.

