7.7 Safety recording instructions

Each subject with an AE occurring after enrollment through study exit should be fully recorded in the source document(s) for further transcription into the eCRF. Each subject should be questioned about AEs at each study visit following randomization and treatment. The question asked should be: "Since your last clinical visit; have you had any health problems?" Information on AEs can also be obtained from signs and symptoms detected during each examination, or from a laboratory test, observations made by the study site personnel, subject diaries, or spontaneous reports from the subjects or their relatives.

When an AE is related to a device deficiency (refer to Section 7.9), including technical device malfunction, the AE shall be recorded on the AE form/module in the eCRF and the technical complaint shall be reported separately on the clinical study complaint form, provided separately in the Investigator file, and the eCRF.

Investigators, or other study site personnel, shall record all AEs in the eCRF, including:

- a) Event term (recorded in standard medical terminology and avoiding abbreviations)
- b) Affected area
- c) Start date (first day with symptoms)
- d) Stop date (last day with symptoms)
- e) Intensity (mild, moderate, or severe according to definition in Section 7.7.1)
- f) Seriousness (serious or not serious, according to definition in Section 7.6.2)
- g) Causal relationship to study product or study product injection procedure (yes or no, see Section 7.7.2)
- h) Action taken (none, medication treatment, non-pharmacological treatment, or other procedures/tests, subject withdrawn)
- i) Outcome of the AE (ongoing, recovered, recovered with sequelae, death, chronic/ stable, not recovered at the end of the study)

The AE form/module in the eCRF must be signed and dated by the Investigator.

The pre-defined, expected post-treatment events shall be assessed separately. These events shall be collected daily by subjects in a diary for up to 28 days after each treatment.

	Title 43USSA2112 CIP Sculptra Decolletage	Doc id
GALDERMA EST. 1981	• 0	MA-50966

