7.8 Safety reporting procedures and timelines

7.8.1 Reporting of Adverse Events (AE)s

AE reporting on each subject shall start upon randomization. The reporting shall continue during each follow-up visit (including telephone contacts and extra visits between planned visits) until the last scheduled visit in the study. All AEs, non-serious as well as serious, must be reported as an AE in the eCRF.

Any events that occur after the subject signs the ICF, but before randomization, will be recorded in the subject's medical history.

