7.8.6 Follow-up of unresolved events ongoing at termination of the study

All serious as well as non-serious AEs with a causal relationship to the study device or treatment procedure and ongoing at study end, shall be followed up after the subject's participation in the study is over. Such events shall be followed-up after the last study visit until resolved, assessed as chronic or stable, or the subject is lost to follow-up. Follow-up information shall be reported on the AE follow-up form.

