#### 2.5.2 Adverse Events (AEs)

All AEs will be coded according to MedDRA and summarized by System Organ Class (SOC), Preferred Term (PT), and treatment. The number of subjects with at least one event, associated percentage, and number of events will be provided.

GALDERMA <small>EST. 1981</small>	Title 43USSA2112 Statistical Analysis Plan - Sculptra Decolletage US PiLot	Doc id MA-55694
---	---	----------------------------------

Effective date: 2023-03-06 14:53

For subject counts, a subject will only be counted once per SOC and once per PT in cases where multiple events are reported for a subject within SOC or PT. For event counts, subjects with multiple events in a category will be counted for each event.

The number of subjects with AEs related to study product or study product injection procedure and unrelated AEs will be presented by SOC, PT, and maximum intensity. Action taken for related AEs will also be summarized by SOC and PT using number of events. AEs related to study product or injection procedure with late onset (> 21 days after most recent treatment session) will be listed.

Serious AEs and AEs of special interest (AESIs) will be listed. **CCI**

For AEs related to study product or study product injection procedure, the number of days to onset and the duration of event will be summarized by SOC and PT using mean, standard deviation, median, minimum, and maximum. Days to onset of an AE will be derived as the start date minus the date of most recent treatment session. Duration of an AE will be derived as the stop date minus the start date + 1. Missing stop date will not be imputed, and therefore no duration will be calculated in these cases.

In addition, a summary of all AEs will be provided, which will include (but is not limited to):

- number of subjects with at least one AE and number of events (in total as well as serious AEs),
- number of subjects with at least one related AE and number of events (in total as well as serious AEs),
- number of subjects with at least one AESI and number of events,
- number of subjects with at least one unrelated AE and number of events (in total as well as serious AEs),
- number of subjects who did not have an AE.

[figure not shown]

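### The adverse event duration summary omits any related event that still has no stop date, so it reads short when the date is missing because the event has not resolved

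*SAP*

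**What the plan says.** Protocol 2.2 lists as the first safety endpoint: "Incidence, intensity, time to onset and duration of Adverse Events (AE)s collected throughout the study period". SAP 1.2.4 repeats it.

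SAP 2.5.2 limits the duration analysis to related events, as does Protocol 9.5, and states that "duration of event will be summarized by SOC and PT using mean, standard deviation, median, minimum, and maximum". Duration is stop date minus start date plus 1. For events without a stop date the rule is: "Missing stop date will not be imputed, and therefore no duration will be calculated in these cases".

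Protocol 7.7 defines the date field as "Stop date (last day with symptoms") and the outcome field as "Outcome of the AE (ongoing, recovered, recovered with sequelae, death, chronic/ stable, not recovered at the end of the study"). Several of those outcomes describe an event that has not ended.

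Under Protocol 7.8.1, routine reporting runs "until the last scheduled visit in the study". Under Protocol 7.8.6, related events still ongoing at study end are then followed "until resolved, assessed as chronic or stable, or the subject is lost to follow-up", and "Follow-up information shall be reported on the AE follow-up form". Protocol 4.4 sends events ongoing at withdrawal to the same section.

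Protocol 9.6 and SAP 2.4.2 provide for missing values to be counted and reported where judged appropriate. SAP 2.1.2 makes the number of subjects a default statistic for quantitative variables and leaves table formats to a companion document.

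**The concern.** Declining to invent a stop date is reasonable. The difficulty is that the rule then treats an unresolved event as if nothing were known about its length. Its start date and the subject's last contact are both recorded, so a minimum duration is known, and for a persistent reaction that minimum may exceed most of the durations in the table.

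Protocol 1.3 says that most of the common reactions (papules, nodules, swelling, induration) resolve with time, so the plan itself allows that some do not. Protocol 1.1 gives tolerability of the larger volume as a reason for the study. A reader of the duration table would want to know how long reactions last, and the events most relevant to that question are the ones the rule can leave out. The maximum is the most exposed figure, because it can be set by a resolved event while a longer one is still running.

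**Working it through.** The documents give no adverse event duration and no share of unresolved events, so there is no plan figure to reproduce. The check has four parts.

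**1. Which events can lack a stop date.** Set Protocol 7.7 beside 7.8.6. The stop date is the last day with symptoms. Post-study follow-up of a related event has three end points: resolution, which supplies a date; a chronic or stable judgement, which need not; and loss to follow-up, which does not. There is also a fourth route: the event resolves after the last visit, but the date on the follow-up form does not reach the locked data. Protocol 10.3 says analyses use the locked datasets, and neither document says whether the follow-up form feeds them.

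**2. What is known about such an event.** Inputs: one month is four weeks (Protocol 3.4), so Month 9 is 9 × 28 = 252 days after baseline, with a window of ±14 days. Sessions are 28 to 42 days apart, so session 4 falls 84 to 126 days after baseline. Minimum duration is last contact minus start plus 1. Take an event that starts 28 days after session 4 and is unresolved at Month 9:

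| Month 9 visit | Session 4 at day 126 | Session 4 at day 84 |
|---|---|---|
| Day 252 | 252 − 154 + 1 = 99 | 252 − 112 + 1 = 141 |
| Day 238 | 238 − 154 + 1 = 85 | 238 − 112 + 1 = 127 |

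These are lengths reached by Month 9. They are lost to the table only if the event still has no stop date in the analysis data. An event that starts 10 days before Month 9 has a minimum of only 252 − 242 + 1 = 11 days, so a missing date does not always mean a long event.

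**3. Direction.** Assume ten events of 10, 20, ..., 100 days (median 55, maximum 100), two of them without a stop date.

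| Events lacking a date | Reported median |
|---|---|
| The two longest | 45 |
| Any two, averaged over all 45 pairs | 55 |
| The two shortest | 65 |

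With the two longest missing, the reported maximum is 80. In general, if a fraction p is unresolved and longest, the reported median is the (1 − p)/2 quantile of all events and the reported maximum is the (1 − p) quantile. For p = 5%, 10% and 20% the median is the 47.5th, 45th and 40th percentile, and the maximum the 95th, 90th and 80th.

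In a small preferred-term cell with assumed durations of 20, 40 and at least 99 days (unresolved), the rule reports median 30 and maximum 40. All three events give median 40 and maximum at least 99.

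**4. Range of size.** Assume exponential durations with mean μ, and that no stop date is gained after Month 9. The second assumption sets aside Protocol 7.8.6, so it overstates the loss if that follow-up yields dates. With follow-up C, the share dropped is exp(−C/μ), and the mean of the rest is μ − C/(exp(C/μ) − 1). C runs from 252 days (onset at baseline) down to 252 − 126 = 126 days (onset at the latest session 4).

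| Assumed μ (days) | Share dropped, C = 252 to 126 | Reported mean, C = 252 to 126 |
|---|---|---|
| 30 | 0.02% to 1.5% | 29.9 to 28.1 |
| 90 | 6.1% to 24.7% | 73.7 to 48.8 |
| 180 | 24.7% to 49.7% | 97.5 to 55.7 |

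For short-lived reactions the rule does almost no harm. It matters only for long-lasting ones.

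**The case against.** The strongest reply is that the plan already limits the damage.

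- Related events are exactly those followed after the last visit, so some that are ongoing at Month 9 will gain a stop date. This stands. A reader might infer that every unresolved reaction drops out, but the documents do not support that: loss is certain only for events with no stop date in the analysis data.
- The plan does provide for counting missing values and shows a number of subjects by default. This also stands, so it would be wrong to say the plan ignores missing data. But the missing-value provision is discretionary. A count of subjects is not a count of events, and neither count shows how long the omitted events had lasted or removes the bias in the mean, median and maximum.
- All data are listed, incidence and intensity are complete, and SAP 2.5 plans no safety inference. This is correct, and it is why the point is modest. The descriptive summaries are nevertheless the whole safety analysis, and duration is a named part of it.
- Some SAP text next to this paragraph, and the place where the other safety analyses would stand, are redacted, and the table formats are in a document not seen here. Nothing can be concluded from those gaps.

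A reader might also infer that the rule will flatter one volume over the other. The documents do not support that. Protocol 1.2 links dilution to how likely nodules are to form, not to how long they last. The shift in the median depends on the fraction of events unresolved, and no passage shows that this fraction differs by arm.

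**Conclusion.** The point holds as a limited one. The stated rule leaves out of a named safety endpoint any related event that still lacks a stop date. When the reason is that the event has not resolved, the reported mean, median and maximum are too short. When the date is missing for another reason, such as onset close to Month 9 or a resolved event with an unknown date, the direction is not fixed.

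The size is unknown. It is nil if all related events resolve with a recorded date, negligible for reactions lasting about a month on average, and material only if long-lasting reactions occur and remain without a date. Every illustrative duration and unresolved share above is an assumption; only the visit timing comes from the documents. No conclusion about a difference between arms is drawn. The effectiveness results and the other safety summaries are not touched.

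**What to change.** In SAP 2.5.2:

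- Label the duration summary as covering related events with a stop date.
- Beside it, by preferred term and treatment group, give the number and percent of related events without a stop date, their recorded outcome, and their minimum duration (last study contact minus start date plus 1), shown as a censored value.
- Report the maximum as at least that value when a censored event is the longest.
- State whether stop dates from the follow-up form in Protocol 7.8.6 enter the table. The endpoint's reference to the study period does not settle this.

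A Kaplan-Meier analysis is not needed. The counts and minimum durations carry the information, and with about 15 subjects per arm (30 randomised 1:1) a median by preferred term would be imprecise.

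The cost is a few sentences and a few table columns. No new data are needed: start date and outcome are recorded for each event (Protocol 7.7), and end of study date and last visit are already listed for each subject (SAP 2.3.1). Before database lock this is an SAP amendment; after it, SAP 2.1 lets a supportive analysis be added and described in the study report. The downside is a busier table and a maximum duration that may look less favourable.

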### 2.5.3 Pre-defined, Expected, Post-treatment Events

The number and percentage of subjects reporting each pre-defined, expected, post-treatment symptom, as collected in the 28-day diary, will be presented in total and by maximum intensity for each treatment session and overall. The number of days with the event for each treatment session will be similarly presented by day category (1, 2-7, 8-14 and 15-28 days). The percentage of subjects with each event also will be plotted for each treatment session by day.

**CCI**

**CC**

Version: 1.0

GALDERMA EST. 1981	Title 43USSA2112 Statistical Analysis Plan - Sculptra Decolletage US PiLot	Doc id MA-55694
------------------------------	---	----------------------------------

## 2.7 Determination of Sample Size

### 2.7.1 Sample Size

The sample size of approximately 30 subjects is not based on a statistical calculation. **CCI**  
[REDACTED]

## 2.8 Changes in the Analysis Planned in the Protocol

There are no changes to the analysis planned in the protocol.

GALDERMA EST. 1981	Title 43USSA2112 Statistical Analysis Plan - Sculptra Decolletage US Pilot	Doc id MA-55694
------------------------------	---	----------------------------------

2023-03-06 14:53

Effective date:

*Effective*

Version: 1.0

GALDERMA EST. 1981	Title 43USSA2112 Statistical Analysis Plan - Sculptra Decolletage US Pilot	Doc id MA-55694
------------------------------	--	---------------------------

CCI

2023-03-06 14:53

Effective date:

*Effective*

Version: 1.0

